#### 4.2 Follow-up Visit Windows

Follow-up visits will be scheduled at appointed times after the date of treatment. The Sponsor recognizes that Subjects may not be able to return for follow-up visits on the exact date required. Thus, a period during which each visit is allowed, i.e., window, is provided below (Table 2). Follow-up visits should be scheduled within the ideal window when possible; however, any available data collected in the analysis windows will be summarized as occurring within the given window. Data collected outside the ideal window, but within the analysis window will not be considered a protocol deviation. Subjects discharged from the hospital before the one month follow-up window (0-22 days post-treatment) are required to return for a one month follow-up visit including radiologic imaging. Subjects discharged during the one month ideal follow-up visit window (23-44 days post-treatment) are not required to return for a one month visit or imaging, provided the required CTA is obtained as part of the discharge assessment.

DICOM imaging collected during the follow-up phase of the study will be provided to the Sponsor for archival purposes. DICOM CT scans will be provided to the Core Lab for analysis.

**CONFIDENTIAL INFORMATION**

**Table 2: Schedule of Follow-up Visits and Time Periods**

Follow-up Visit	Ideal Window (days)	Analysis Window (days)
Procedure	0	0
Discharge*	Before hospital discharge	N / A
Post-Procedure	Not required	1-14
1 Month	23-44	15-59
6 Months	150-210	60-242
12 Months	275-455	243-546
24 Months	640-820	547-911
36 Months	1005-1185	912-1275
48 Months	1370-1550	1276-1640
60 Months	1735-1915	1641-2006

\*Follow-up visit is categorized as "Discharge" through initial hospitalization, regardless of length.

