	
Device integrity - Absence of the following events through one year of follow-up:
 
 • Loss of functional patency in any branch component due to thrombus or mechanical failure of the branch components • Loss of functional patency in the main body component(s) due to thrombus or mechanical failure of the main body component(s) • Separation of the branch components from the main body component(s) • Separation of the main body component(s) from the accessory components (Distal Bifurcated Component and / or contralateral limb components) 
Individual components of technical success Individual components of device integrity at one month, six months and one year follow-up Patency (Primary, Assisted Primary and Secondary) Absence of Type I and Type III endoleaks at one month follow-up

Subject Population	Subjects with Thoracoabdominal Aortic Aneurysms Involving the Visceral Branch Vessels
Number of Subjects Treated	10
Number of Sites	Six in the United States
Expected Time to Complete Enrollment	18 Months
Schedule of Events	
Assessments at Pre-treatment:
 
 • CT of chest, abdomen and pelvis • Physical exam • Creatinine measurement 
Assessments at Treatment:
 
 • Angiography 
Assessments at Hospital Discharge:
 
 • Physical exam • Creatinine measurement • Abdominal ultrasound (optional) 
Assessments at Follow-up (One month, six months, and annually through 5 years):
 
 • CT of chest, abdomen and pelvis (not required at hospital discharge) • Lumbar spine series X-ray (4 views) (annual follow-up only)* • Physical exam • Creatinine measurement • Abdominal ultrasound (optional) 
*As enrollment is closed for this study, for all subjects that have completed their one year follow-up prior to this protocol amendment being implemented, subjects will be

CONFIDENTIAL INFORMATION

	expected to have radiograph assessments at their next annual follow-up exam (i.e. two year follow-up) and annually thereafter.
Anticipated Total Study Duration	7 years from initiation of enrollment

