**CONFIDENTIAL INFORMATION**

### 2.3.2 Secondary Endpoints

Secondary endpoints include the following:

- Technical Success, including individual components of technical success
- Device Integrity, including Individual components of device integrity
- Patency (Primary, Assisted Primary, and Secondary)
- Absence of Type I and Type III endoleaks at one month follow-up

Technical success is defined as:

- Successful access to the necessary arterial sites
- Successful deployment of all required TAMBE Device components and any required accessory components
- Patency of all required TAMBE Device components and any required accessory components on completion angiography
- Absence of surgical conversion within 24 hours of initiation of the procedure

Device integrity will be defined as freedom from all of the following events in the first year of follow-up.

- Loss of functional patency in any treated branch component due to thrombus or mechanical failure of the branch component
- Loss of functional patency in the main body component(s) due to thrombus or mechanical failure of the main body component(s)
- Separation of the treated branch components from the main body component(s)
- Separation of the main body component(s) from the accessory components (Distal Bifurcated Component Device and / or Contralateral Leg Components)

The definitions for device integrity in Appendix A of the protocol were based on the proposal outlined in Chaikof et al.[1]. These events will be adjudicated by a CEC. Device integrity and its individual components will be reported at interim follow-up time points as well, including one and six months.

Patency will be assessed using Kaplan-Meier analysis. Subjects not experiencing an event will be censored at time of last follow-up or contact. Subjects having events are defined below:

- Primary patency - Blood flow without occlusion maintained through the device after implant without an intervention. Subjects who have a reintervention on a treated segment before occlusion to prevent eventual loss of patency, after occlusion to restore patency, or open surgical bypass to restore patency will have lost primary patency at the earliest such reintervention.

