#### 5.4.2 Core Laboratory

An independent Core Laboratory (Core Lab) will provide review of imaging data collected during the study at pre-treatment and follow-up.

Summaries of qualitative Core Lab imaging findings (endoleak, wire fracture, component separation, patency, and rupture) will be provided at each analysis window. The denominator for each category will be the number of subjects with a CT imaging assessment in the given window which is read by the Core Lab.

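### Does the Discharge footnote to Table 2 remove a day 23–44 discharge CTA from the one-month imaging results?

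*SAP*

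**What the plan says.** Five places bear on this.

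- **SAP Table 2, Discharge row and footnote.** The ideal window is "Before hospital discharge" and the analysis window is N / A. The footnote adds: "Follow-up visit is categorized as 'Discharge' through initial hospitalization, regardless of length".
- **SAP 4.2, the rule for data.** Section 4.2 says that "any available data collected in the analysis windows will be summarized as occurring within the given window". Table 2 gives 1 Month an analysis window of days 15–59 and an ideal window of days 23–44.
- **SAP 4.2, the waiver.** Subjects discharged in the one-month ideal window "are not required to return for a one month visit or imaging, provided the required CTA is obtained as part of the discharge assessment".
- **SAP 5.4.2.** Core Lab findings, endoleak among them, are summarized at each analysis window. The denominator is "the number of subjects with a CT imaging assessment in the given window which is read by the Core Lab".
- **Imaging schedule.** SAP Table 1 has no CT under Hospital Discharge. The Schedule of Events in the Protocol Summary agrees: "CT of chest, abdomen and pelvis (not required at hospital discharge".

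The output at issue is the secondary endpoint in SAP 2.3.2: "Absence of Type I and Type III endoleaks at one month follow-up".

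**The concern.** The waiver places a subject's only required one-month scan inside a visit that the footnote calls Discharge, and Discharge has no analysis window. No sentence says whether the label or the study day prevails. A programmer who windowed by visit label would leave that CTA unassigned. Neither document schedules a CT at discharge, so there would be no other imaging row to hold it.

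The subject would then be missing from the one-month endoleak endpoint and from the one-month Core Lab tables, even though section 4.2 accepts the scan in place of one-month imaging. The study is small (10 subjects in the Protocol Summary, an estimated maximum of 20 in SAP 2.2) and purely descriptive, so one scan could decide whether any one-month endoleak is reported.

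The 30-day primary endpoint and Kaplan-Meier patency depend on event and censoring dates and are not affected by the visit label.

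**Working it through.** The plan gives no figure to reproduce here. The check is to apply its rules to a CTA taken in hospital on days 23–44, and then to size the loss if the label reading were used instead.

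**1. Which window does the scan fall in?** The analysis windows in Table 2 are 0, 1–14, 15–59, 60–242, 243–546, 547–911, 912–1275, 1276–1640 and 1641–2006. Each begins the day after the previous one ends, so days 0 to 2006 are covered without gap or overlap. Every day from 23 to 44 lies in 15–59 and in no other window. By study day the scan is 1 Month.

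**2. What does each rule govern?** The footnote governs how a *visit* is categorized. The rule in section 4.2 governs where *data* are summarized, and it makes no exception for data collected before discharge. N / A in the Discharge row fits this: Discharge is a visit with no day range, so it does not compete with the day windows. The Post-Procedure row points the same way. It has an analysis window (days 1–14) although no visit is required, so a window can exist without a scheduled visit of its own.

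**3. Which CTA does the waiver mean?** Table 1 and the protocol require no CT at discharge. The required CTA in the waiver can therefore only be the one-month CTA, done before the subject leaves hospital. On the label reading the SAP would accept a scan in place of the one-month scan and then leave it out of the one-month results.

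**4. What does the Core Lab denominator use?** Section 5.4.2 counts subjects with a Core Lab-read CT in the window. A day-30 CT meets that test whatever the visit is called.

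**5. Size, if the label reading were applied anyway.** Let N be the number of subjects and k the number discharged on days 23–44 whose only one-month CTA was done in hospital. The documents do not give k, so k = 1 is assumed. All other subjects are taken to have a one-month scan, and one Type I or III endoleak is assumed in total. By study day the rate is 1/N. By label it is 0/(N − k) if the endoleak is in the excluded subject, and 1/(N − k) if it is in another.

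| N | By study day | By label, endoleak in the excluded subject | By label, endoleak in another subject |
|---|---|---|---|
| 10 | 1/10 = 10.0% | 0/9 = 0% | 1/9 = 11.1% |
| 20 | 1/20 = 5.0% | 0/19 = 0% | 1/19 = 5.3% |

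With k = 0 nothing changes.

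**6. How likely is the damaging column?** Let p be a subject's chance of discharge on days 23–44. If endoleak and length of stay are independent (an assumption), then given a single endoleak the chance that it sits in such a subject is p, at either N. For assumed values of p of 2%, 5% and 10%, that is 2%, 5% and 10%. If endoleak and a long stay tend to occur together, the chance is higher.

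**The case for a change.** The best case for a change is textual. The footnote covers stays of any length, so it cannot be confined to short ones, and its row has no analysis window. The SAP nowhere says that Discharge is only a label; that has to be inferred. The sponsor wrote a rule for discharge on days 23–44 and so thought the case possible. In a descriptive study the counts are the result, and one sentence fixed in advance would remove any temptation to choose a window after the scan has been read.

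Part of this stands: no sentence states precedence, and the footnote sits awkwardly beside section 4.2. What does not stand is that the two readings are evenly matched. The rule for data, the waiver, the imaging schedule and the Core Lab denominator all lead to the study-day reading. Only the footnote points the other way, and it does not speak about summarizing data.

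A related point is that an inpatient CT on days 15–22 followed by the required return scan would put two CTs in the 1 Month window. Repeat scans can arise in any analysis window, so that is a separate question which the footnote does not create.

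**Conclusion.** The concern does not call for a change. This is a missing line of detail that an analyst following SAP 4.2 and 5.4.2 fills correctly: a discharge CTA on days 23–44 is assigned by study day and counted as 1 Month. On that reading the loss is zero.

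A shift from 10.0% or 5.0% to 0% needs three things together: windowing by visit label against section 4.2, at least one discharge on days 23–44, and the study's only Type I or III endoleak in that subject. The first runs against the plan's text. The documents give no rate for the other two, so the sizes shown rest on the assumed k = 1, the assumed p of 2–10% and independence of endoleak and length of stay. If the endoleak is in another subject, the difference is about one percentage point or less. Only a descriptive secondary endpoint and the one-month Core Lab tables are exposed, and no hypothesis is tested.

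Saying that Discharge is a visit label and that imaging is windowed by study day would record what the plan already implies, without altering any result.

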#### 4.3 Data and Safety Monitoring Board

An independent Data and Safety Monitoring Board (DSMB) will advise the Sponsor regarding the continuing safety of study Subjects. The AAA 13-02 DSMB will be comprised of an interdisciplinary team of members with pertinent expertise in vascular and / or cardiothoracic surgery who are not directly involved in the conduct of the study. The members will be compensated for their involvement in the DSMB, including reimbursement for reasonable travel expenses to attend meetings.

This committee will operate under pre-specified procedures and timelines as outlined in the DSMB Charter. The DSMB will be responsible for conducting periodic reviews of aggregate data on a prescribed basis. The frequency of data review and other roles and responsibilities of the DSMB will be specified in the DSMB Charter.

Based on the safety data, the DSMB will make recommendations to the Sponsor. Recommendations may include study termination, study continuation with or without major or minor modifications, temporary suspension of enrollment and / or study intervention until some uncertainty is resolved. All final decisions regarding study modifications rest with the Sponsor.

#### 4.4 Clinical Event Committee

A Clinical Events Committee (CEC), consisting of the six participating Investigators will ensure consistent and accurate AE and death reporting and classification. No study Investigators on the CEC will review events from their Institution. CEC will adjudicate selected safety AEs according to the definitions provided in Appendix A of the protocol.

This committee will operate under pre-specified procedures and timelines as outlined in the CEC Charter. Selected summaries of the safety events outlined in the protocol will be prepared based on the CEC adjudication.

**CONFIDENTIAL INFORMATION**

The CEC will be responsible for review and adjudication of key AEs in the AAA 13-02 study. Specifically:

- The CEC will review reported AEs which potentially meet the definition of a primary safety endpoint event. The CEC will adjudicate the AEs provided to them against the definitions in Appendix A of the protocol and make a final determination of the AE against the available endpoints. Primary safety endpoint events to be adjudicated include death, stroke, myocardial infarction, bowel ischemia, paraplegia, respiratory failure, and renal failure.
- The CEC will review reported AEs which potentially meet the definition of device integrity endpoints through one year of follow-up including loss of functional patency in any branch component due to thrombus or mechanical failure of the branch components, loss of functional patency in the main body component(s) due to thrombus or mechanical failure of the main body component(s), separation of the branch components from the main body component(s), or separation of the main body component(s) from the accessory components (DBC and / or contralateral limb components).
- The CEC will adjudicate events they receive as serious or non-serious for primary safety, device integrity, and any other events that are forwarded for adjudication.
- Additional events may be chosen to be adjudicated by CEC members if deemed necessary by the study team.

The members may be compensated for their involvement in the CEC, including reimbursement for reasonable travel expenses to attend meetings.

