### 2.3 Study Endpoints

#### 2.3.1 Primary Endpoint

The primary endpoint of the study will be procedural safety defined as the absence of the following events through 30 days post-procedure:

- Death
- Stroke
- Myocardial Infarction
- Bowel Ischemia
- Paraplegia
- Respiratory Failure
- Renal Failure
- Procedural Blood Loss  $\geq 1000$  mL

These events will be adjudicated to the definitions provided in Appendix A of the protocol by a CEC.

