## 5.0 Statistical Analyses

### 5.1 Analysis Populations

All enrolled Subjects will be included in reported data.

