### 5.3 Statistical Analysis of Endpoints

Due to the exploratory nature of this study, statistical analysis will be limited to summary statistics, including frequency counts for categorical variables, and measures of dispersion for continuous variables. No inferential analysis will be performed.

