#### 5.5.4 Subject Death

Death is not an adverse event but instead an outcome of an AE. Any ongoing or unresolved AEs at the time of death will be indicated as ongoing/continuing on the case report form. Attempts should be made by the investigative Site to obtain death certificates, autopsy reports and device explants when at all possible.

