## 6.0 Interim Analyses and Safety Monitoring Analyses

Safety data will be periodically reviewed by a Data Safety and Monitoring Board (DSMB). A comprehensive summary of all reported adverse events will be reviewed. Specific adverse events of clinical interest in this patient population will include, but are not limited to stroke, myocardial infarction, bowel ischemia, paraplegia, respiratory failure, renal failure, or those attributable to loss of patency in the main body or branch components.

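### Does leaving procedural blood loss of 1000 mL or more off the events committee's list put the primary endpoint at risk?

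*SAP*

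**What the plan says.** The Protocol Summary (Study Endpoints) and SAP 2.3.1 give the same eight components of 30-day procedural safety: death, stroke, myocardial infarction, bowel ischemia, paraplegia, respiratory failure, renal failure, and procedural blood loss of 1000 mL or more. SAP 2.3.1 then adds, without exception: "These events will be adjudicated to the definitions provided in Appendix A of the protocol by a CEC".

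SAP 4.4 describes the committee's work more narrowly. Its general statement is "CEC will adjudicate selected safety AEs according to the definitions provided in Appendix A of the protocol". The first bullet on its duties says "The CEC will review reported AEs which potentially meet the definition of a primary safety endpoint event", and continues: "Primary safety endpoint events to be adjudicated include death, stroke, myocardial infarction, bowel ischemia, paraplegia, respiratory failure, and renal failure". Blood loss is not in that list. Later bullets let the committee handle other forwarded events, and let the study team pick further events for adjudication.

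On analysis, SAP 5.3 limits the work to summary statistics: "No inferential analysis will be performed".

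**The concern.** Two sections describe adjudication of the only primary endpoint, and they disagree on one component. That component is also the one most exposed to the disagreement. It is a measured quantity, and a site may log a volume on a procedure form without reporting it as an adverse event. If the committee sees only reported adverse events, and the composite is assembled from its determinations, a subject whose sole event was a blood loss of 1000 mL or more could be tabulated as free of events, contrary to the definition. In a study this small, one subject visibly changes the headline rate.

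SAP 6.0 seems to point the same way. Its events of clinical interest are "stroke, myocardial infarction, bowel ischemia, paraplegia, respiratory failure, renal failure, or those attributable to loss of patency in the main body or branch components", again without blood loss.

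**Working it through.** The plan gives no figure to reproduce here, so the check is a comparison of lists followed by one line of arithmetic.

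**Lists side by side**

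| Component | Protocol Summary | SAP 2.3.1 | SAP 4.4 | SAP 6.0 |
|---|---|---|---|---|
| Death | yes | yes | yes | no |
| Stroke | yes | yes | yes | yes |
| Myocardial infarction | yes | yes | yes | yes |
| Bowel ischemia | yes | yes | yes | yes |
| Paraplegia | yes | yes | yes | yes |
| Respiratory failure | yes | yes | yes | yes |
| Renal failure | yes | yes | yes | yes |
| Blood loss of 1000 mL or more | yes | yes | no | no |
| Count | 8 | 8 | 7 | 6 |

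SAP 4.4 differs from SAP 2.3.1 by exactly one item (8 − 7 = 1). SAP 6.0 bears little on the question: it concerns monitoring by the data and safety board, is expressly not exhaustive, adds an item outside the primary endpoint (loss of patency), and follows a promise to review all reported adverse events.

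**Size if one subject were misclassified**

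Shift in the event-free proportion = 1/n.

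- n = 10 (Protocol Summary, number treated): 1/10 = 10 percentage points.
- n = 20 (SAP 2.2, estimated maximum treated): 1/20 = 5 percentage points. With fewer than 20 subjects the shift would be larger.

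These are illustrations on planned treated counts. SAP 5.1 says "All enrolled Subjects will be included in reported data", which does not fix the denominator of the primary endpoint. The documents give no rate of large blood loss, so no probability can be attached.

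**What must hold for the error to occur**

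1. The composite is built only from committee determinations. No section says so. SAP 4.4 says only that some selected summaries will rest on adjudication.
2. Blood loss is the subject's only primary event. Otherwise the subject is already a failure.
3. The loss is not reported as an adverse event. SAP 5.5 defines adverse events broadly and SAP 5.5.3 asks for all of them from enrollment on. A loss of a litre or more could well qualify, and the first bullet in SAP 4.4 would then bring it to the committee.
4. Nobody forwards it under the other bullets of SAP 4.4.
5. The analyst overlooks that SAP 2.3.1 names the component with its threshold.

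All five are needed together.

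**The case for a change.** The best case for a change is that either reading leaves one section wrong. If a measured volume needs no adjudication, SAP 2.3.1 overstates the committee's role; if it does, SAP 4.4 is incomplete. The verb *include* may signal an open list, but the neighbouring bullet on device integrity uses the same kind of wording and then names all four of its components, so seven out of eight looks like an omission. The route for additional events is discretionary, whereas SAP 2.3.1 is unconditional. No supplied text says that crossing 1000 mL must be reported as an adverse event.

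The inconsistency stands. The inference to a wrong result does not. The restriction to adverse events is not applied literally even within the SAP: section 5.5.4 states "Death is not an adverse event but instead an outcome of an AE", yet death heads the list in SAP 4.4. That point is only partial, since a death will normally come with a reported event and a measured volume need not. More telling is the nature of the component. Stroke or bowel ischemia calls for clinical judgement against a definition; a volume at or above 1000 mL calls for a comparison with a number. The natural reading is that the sentence in SAP 2.3.1 is slightly over-inclusive and that SAP 4.4 lists the events needing judgement.

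**Conclusion.** No change to the plan follows. The two sections differ by one component out of eight, which is a clerical slip. An analyst following SAP 2.3.1 would score blood loss from the procedural volume against the stated threshold, count the subject as a failure, and report the intended descriptive rate. Aligning the sentences would be harmless tidying, but it would not alter the endpoint, the threshold, or any result shown to be at risk.

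The 5 to 10 points per subject is the size of a hypothetical error, not an expected one.

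This conclusion assumes that the procedural volume is recorded and available to the analyst. The supplied documents neither confirm nor deny that. Appendix A of the protocol, the CEC Charter and the case report forms were not available, and they may state the route outright. The conclusion would change if one of them showed that the composite is taken solely from committee determinations and that blood loss reaches the committee only when a site reports it as an adverse event.
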